The Apos Device. (a) Biomechanical device comprising two individually calibrated elements and a foot-worn platform. The elements are attached to a platform under the hindfoot and forefoot regions. (b) The biomechanical elements are available in different degrees of convexity and resilience. (c) The specially designed sole of the platform includes two mounting rails and a positioning matrix to enable flexible positioning of each biomechanical element. [Elbaz, 2014].

Figure 2. The sham device

CONFIDENTIAL

This material is the property of the NYU School of Medicine and Langone Medical Center. Do not disclose or use except as authorized in writing by the study sponsor

Objectives and Hypothesis of Study

1. The primary objective is to evaluate the efficacy of AposTherapy® at 6 months, with the primary efficacy assessment based on improvement in knee pain score and improvement in function in patients with knee OA. The hypothesis is that patients fitted with the calibrated AposTherapy® device will demonstrate an improvement in knee pain intensity and improvement in function compared to patients who are fitted with a sham-placebo Apos device.
2. After completion of 6 months of therapy, patients will be un-blinded to their group allocation and the second phase of the study will commence, including the following aims:
 - a. To evaluate the long-term (12 months) effect of AposTherapy® on the level of pain and the level of function of patients with knee OA. We hypothesize that patients will maintain the diminished levels of pain and improved function.
 - b. To evaluate the changes in the level of pain and the level of function of patients that were originally allocated to the control group and will now cross-over and commence AposTherapy® treatment for 6 months. We hypothesize that patient will report an improvement in the level of pain and improvement in function following 6 months of treatment.

Primary Efficacy Endpoints

- Phase I:
 - Improvement in knee pain score and improvement in function, as measured by change from baseline Western Ontario and McMaster University (WOMAC) score to 6 months post treatment.
- Phase II:
 - Long-term effect (12 months) of AposTherapy on pain and function, as measures by WOMAC, of patients with knee OA
 - Improvement in knee pain and knee function, as measured by WOMAC, of patients with knee OA that were allocated to the sham control group and have crossed-over to the active group, receiving AposTherapy for 6 months.

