- Patients who have had a joint replacement or other major surgery to the knee, hip or ankle (ipsilateral or contralateral side).
- Patients suffering from neuropathic arthropathy.
- Patients with an increased tendency to fall.
- Patients exhibiting a lack of physical or mental ability to perform or comply with the study procedure.
- Patients with a history of pathological osteoporotic fracture.
- Patients suffering from symptomatic degenerative arthritis in lower limb joints other than the knees.
- Patients with referred pain in the knees from primary back or hip joint pain.
- Patients with neurological deficits to the lower extremity (ex. foot drop)
- Patients whose shoe size is less than US 4 and greater than US 12
- Patients who have had arthroscopy within 6 months of the study
- Patients with inflammatory arthropathy
- Patients with any central nerve system disease/neurological problem (i.e. Parkinson's, post CVA (stroke), etc.).

Vulnerable Subjects

We do not intend to enroll vulnerable subjects.

Subject Withdrawal

Patients are free to withdraw at any time from the study. While participating in the study, patients should avoid any other treatment modality apart from rescue pain medication (Acetaminophen/Paracetamol) as long as it is possible. If patients require injection therapy or surgery on the study knee(s) during the course of the study, the patient will be withdrawn from further data collection.

III. METHODS AND PROCEDURES

Sample Size Analysis

Assuming normality on the data, we calculated the statistical power for various detectable effect sizes listed in Table X using PASS 2011 software (http://www.ncss.com/download_PASS11.html). The analysis of power is performed conservatively by assuming the largest variability in pain scores observed in the preliminary data (e.g., reduction of pain scores of 3.0 in active group and 0 of control group with a pooled standard deviation of 3.60 corresponds to an effect size of 0.8. After accounting for a 10% loss to follow-up we would expect to enroll 60 patients in each group for a total of 120 patients. With 120 samples (60 each), the two-sided t-test will have 80% power at the 0.05 significance level to detect differences of pain score of 0.8 SD units between control and case [Bar-Ziv, 2013].

Methods and Procedures

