Phase I - A prospective, interventional, randomized, double-arm clinical evaluation study. Patients over the age of 45 years who come into the office with symptomatic knee pain, and a Kellgren-Lawrence grade more than or equal to grade 2, and have pain levels above 2\10 may be included in the study.

Patient progress will be monitored for a six (6) months period, consisting of information from office visits and scores obtained at each study visit. Patients will be asked to return to the physician's office at specific time points (3 months and 6 months after the initial visit). After signing consent patients will be randomized to one of two groups:

- **Group 1: AposTherapy® Active Arm**
- **Group 2: AposTherapy® Control Arm**

Randomization Process

Blocked randomization will be used to assign subjects to their respective treatment arms. The allocation ratio will be one to one and the random method of selection will be through a computerized random

CONFIDENTIAL

This material is the property of the NYU School of Medicine and Langone Medical Center. Do not disclose or use except as authorized in writing by the study sponsor

number generator. The on-site coordinator will be responsible for entering and maintaining the subject randomization information. After randomization has been completed, research personnel will review and document the patient's demographics, medical, and surgical history on the study case report forms. The baseline patient-reported outcome questionnaires will then be completed (these include the WOMAC, VAS, SF-36). The physician and research team will then perform a clinical evaluation of the knee.

Active Arm Process

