- Stability: McMurray test; Apley's Grind test, patellar tilt test, patellar grind test, patellar apprehension test
- Strength: Muscle strength (quadriceps, hamstrings, Iliopsoas)
- Range of Motion: Passive and active ROM.
- Sensation: Reflexes, function, sensation, etc. (normal/abnormal)
- Posture/alignment: leg length discrepancy, foot position, etc.
- Standard Radiographic Testing: AP and Lateral x-ray views of the knee (to determine K-L grade)
These x-rays are part of the standard practice when examining patients who present with osteoarthritis of the knee;
- Complete Patient Reported Outcome Questionnaires:
 - Western Ontario and Mac Master University (WOMAC)
 - Visual Analogue Scale (VAS) pain tool
 - Short-Form 36 (SF-36)
 - Creation of a treatment plan for the patient (time of usage, instructions of use etc...)

The following standard of care procedures will be conducted at the treatment center located at [name]:

- AposTherapy® device calibration according to patient's allocation

VISIT 3 & 4 – Three and Seven Week Follow Up

The following standard of care procedures will be conducted at the treatment center located at [name]:

- AposTherapy® device adjustment

VISIT 5 – 12 Weeks (3 Month) Follow Up (between 76-104 days after baseline)

The following procedures will be conducted at the physician's office located at NYULMC Center for Musculoskeletal Care, [name]):

- Physical Knee Evaluation (same as screening/baseline)
- Adverse/Reportable Event review
- Review concomitant medications
- Complete Patient Reported Outcome Questionnaires:
 - Western Ontario and Mac Master University (WOMAC)
 - Visual Analogue Scale (VAS) pain tool
 - Short-Form 36 (SF-36)
- Compliance Follow-Up

The following standard of care procedures will be conducted at the treatment center located at [name]:

- AposTherapy® device adjustment

VISIT 6 – 18 Weeks Follow Up

The following standard of care procedures will be conducted at the treatment center located at [name]:

- AposTherapy® device adjustment

VISIT 7 – 24 Weeks (6 Month) Follow Up (between 150-210 days after baseline)

The following procedures will be conducted at the physician's office located at NYULMC Center for Musculoskeletal Care, [name]):

CONFIDENTIAL

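### The plan names no primary model or missing-data method for Phase I, and the only test it names would, at month 6, ignore the month-3 WOMAC of patients lost later

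*Combined protocol and SAP*

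**What the plan says.** All places are in the combined protocol and SAP.

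- **Section III, Sample Size Analysis** (repeated in the Study Summary): "After accounting for a 10% loss to follow-up we would expect to enroll 60 patients in each group for a total of 120 patients". It adds that "the two-sided t-test will have 80% power at the 0.05 significance level" for a 0.8 SD difference in pain score. No visit is attached to that test.
- **Section I, Primary Efficacy Endpoints, Phase I**: knee pain and function, "as measured by change from baseline Western Ontario and McMaster University (WOMAC) score to 6 months post treatment".
- **Section I, Secondary Efficacy Endpoints, Phase I**: WOMAC across all time points, including month 3, is secondary.
- **Section III, Visit 5 and the study schedule**: WOMAC is collected from both arms at week 12 (days 76 to 104) and again at week 24.
- **Section III, Data Analysis, Phase I**: the primary outcome is described as a comparison of WOMAC scores at baseline, month 3 and month 6. No test, model, analysis population or rule for missing values is given.

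**The concern.** Extra enrolment replaces lost precision. It does nothing about who is lost. In this trial both arms are asked to wear a device for about two hours a day and to attend repeated fitting visits, and patients may leave at any time. Lack of relief by month 3 is a plausible reason to stop attending. It could act differently in the two arms: the sham has no biomechanical elements, but sham patients receive the active device after month 6, which may keep them in.

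A patient who leaves between months 3 and 6 has a recorded month-3 WOMAC that predicts the missing month-6 value. A comparison of month-6 change among completers ignores it. If such loss is uneven, the estimated device effect is shifted, and the direction cannot be known beforehand.

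Because the plan fixes no model, the choice between a completer test and one that uses month 3 could be made after the data are seen. The role of month 3 is also unsettled: it is secondary in the endpoint list but inside the primary comparison in Data Analysis.

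**Working it through.** **1. The plan's own figures.** The inputs are "reduction of pain scores of 3.0 in active group and 0 of control group with a pooled standard deviation of 3.60", a ratio of 3.0/3.60 = 0.833, stated as 0.8; 10% loss; and 60 per arm at 1:1.

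- Patients expected at month 6: 60 × 0.9 = 54 per arm.
- Two-sided t-test at 0.05 with effect 0.8 SD: power is 98.5% with 54 per arm and 99.1% with 60.
- The stated 80% power is not reproduced. It needs 26 per arm, or 26/0.9 = 28.9, so 29 after loss. That is a separate matter. Here it shows only that precision at the planned effect is ample, so the issue is bias.

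**2. Bias of a completer comparison.** Let the month-3 and month-6 WOMAC changes be normal with SD 1 and correlation ρ, with higher meaning less improvement. If loss depends only on the month-3 value, the mean month-6 change among completers in an arm is displaced by ρ × s. Here s is the displacement of the completers' mean month-3 value. The bias of the arm difference is therefore ρ × (s for device − s for sham).

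Assumptions, none given in the documents: all loss falls after month 3; loss is 5% in one arm and 15% in the other; ρ is 0.5 to 0.7; and the log-odds of loss rise by 0.5, 1 or 2 per SD of month-3 change. The values of s come from numerical integration.

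| Slope | s at 5% loss | s at 15% loss | Difference | Bias, ρ = 0.5 | Bias, ρ = 0.7 |
|---|---|---|---|---|---|
| 0.5 | −0.025 | −0.073 | 0.048 | 0.024 | 0.034 |
| 1 | −0.047 | −0.133 | 0.086 | 0.043 | 0.060 |
| 2 | −0.077 | −0.203 | 0.126 | 0.063 | 0.088 |

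The range is about 0.02 to 0.09 SD. If sham loses more, its completers look better and the device effect is understated. If the device arm loses more, the effect is overstated. With equal loss and equal slope the two s values cancel and the bias is zero.

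**3. Scale.** The standard error of the difference with 54 per arm is √(2/54) = 0.192 SD. The bias is therefore 0.024/0.192 = 0.13 to 0.088/0.192 = 0.46 of a standard error. Against the planned 0.8 SD it is 3% to 11%. At SD 3.60 it would be about 0.09 to 0.32 points, but that SD belongs to a preliminary pain score and is not shown to be the SD of WOMAC change.

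**4. A milder and a harsher case.**

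- Same loss rule in both arms, 10% loss overall, device effect 0.5 SD at month 3: loss splits from 8.9% v 11.1% (slope 0.5) to 6.9% v 13.1% (slope 2), with sham higher. The bias runs from 0.5 × (0.054 − 0.044) = 0.005 to 0.7 × (0.181 − 0.103) = 0.055 SD, always an understatement.
- The worst 10% of one arm at month 3 are lost, and loss in the other arm is random: s = 0.1755/0.9 = 0.195 in size, so the bias is 0.06 to 0.14 SD for ρ of 0.3 to 0.7.

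**5. What using month 3 does.** When loss depends only on observed month-3 values, a likelihood analysis that includes month 3 brings the bias to about zero in all these cases. The gain in precision is small. The variance per arm is (1 − ρ²)/54 + ρ²/n₃, where n₃ is the number seen at month 3. With all six losses after month 3 (n₃ = 60) and ρ = 0.7, this is 0.51/54 + 0.49/60 = 0.0176, an effective 56.8 per arm instead of 54.

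**The case against.** The strongest reply is that the documents never commit to a month-6 completer t-test. A reader might infer that they do, and that patients lost after month 3 are therefore excluded. The documents do not support that. The t-test appears only in the power calculation, sizing a trial with a t-test does not bind its analysis, and Data Analysis places month 3 within the primary comparison. This stands, so the defect is an unspecified primary model and missing-data method, with one named test that would drop these patients if carried over to the stated endpoint.

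A second reply is that the size depends on chosen inputs. This also stands. The 5% v 15% split, the slope and the correlation are assumptions; the plan gives only 10% overall. A reader might take 0.09 SD as the expected bias, but it needs steep dependence and the higher correlation, and a common loss rule in both arms gives less.

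Third, the remedy is partial. The documents do not say when losses occur, so it cannot be assumed that most lost patients will have a month-3 value. If half the loss comes before month 3 with the same dependence, the repeated-measures estimate would itself be off by about 0.01 to 0.04 SD. Loss driven by unobserved outcomes is not corrected either. These limits call for a sensitivity analysis. They do not favour a completer test, which uses less of the data and needs a stronger assumption.

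**Conclusion.** The concern holds as a gap in specification with a plausible, modest bias behind it. Loss is covered only by enrolment, Data Analysis gives no model or missing-data rule, and the only named test, applied to the primary endpoint, would ignore month-3 WOMAC already collected.

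Under 5% v 15% loss that depends on month-3 change, with ρ of 0.5 to 0.7, the bias would be about 0.02 to 0.09 SD in either direction, under half a standard error. It is about zero with equal loss. It rests on normality, on all loss falling after month 3, and on loss depending only on the observed month-3 value.

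A reader might also infer that the trial would lose power; at the planned effect it would not. The change should be made because it is cheap and removes a choice otherwise open after the data are seen, not because the trial's result would be overturned.

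**What to change.** In Data Analysis, Phase I:

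- **Primary model.** Name a mixed model for repeated measures of WOMAC change at months 3 and 6, in all randomised patients with any post-baseline value, with arm, visit, arm-by-visit and baseline WOMAC as terms and an unstructured covariance.
- **Primary comparison.** Make the active-minus-sham contrast at month 6 primary for the WOMAC pain and function measures named in the endpoint section, and month 3 secondary. This reconciles the primary endpoint, the secondary endpoint list and Data Analysis. State whether both measures must succeed or how the error rate is shared.
- **Missing data.** State the assumption that loss is explained by observed values. Add a sensitivity analysis for loss that is not, covering patients with no post-baseline value. Keep the month-6 completer comparison as supportive.
- **Reporting.** Give the number lost before and after month 3, by arm.

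The cost is wording and some analysis programming, with no new visits, data or patients. The downside is reliance on an assumption about loss that cannot be verified from the observed data, and no help from the model for patients lost before month 3; hence the sensitivity analysis.

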Secondary Efficacy Endpoints

- Phase I:
 - Improvement in WOMAC scores between all study time points – pre-treatment and following 3 months and 6 months post-treatment;
 - Improvement in Visual Analog Score (VAS) score between all study time points;
 - Improvement in Short-Form 36 (SF-36) score between all study time points;
 - Reduction in usage of pain killers or NSAIDS
- Phase II:
 - Original Active group - Improvement in knee pain and knee function scores, as measured by change from baseline WOMAC score to 12 months post treatment;
 - Original Active group - Improvement in VAS score between baseline and 12 months post treatment;
 - Original Active group - Improvement in SF-36 score between baseline and 12 months post treatment;
 - Original Active group - Reduction in usage of pain killers or NSAIDS
 - Cross-over group - Improvement in WOMAC scores between all study time points – pre-treatment and following, 3 months and 6 months post-treatment;
 - Cross-over group - Improvement in Visual Analog Score (VAS) score between all study time points;
 - Cross-over group - Improvement in Short-Form 36 (SF-36) score between all study time points
 - Cross-over group - Reduction in usage of pain killers or NSAIDS

CONFIDENTIAL

This material is the property of the NYU School of Medicine and Langone Medical Center. Do not disclose or use except as authorized in writing by the study sponsor

Outcome Measure Evaluation Criteria

Western Ontario and Mac Master University (WOMAC) – the WOMAC is a self-administered osteoarthritis outcomes instrument designed to assess lower extremity pain and function in osteoarthritis of the knee or hip. The minimal clinically important difference (MCID) proportion is a 16.0% reduction in WOMAC [Hmamouch, 2014].

Visual Analog Score (VAS) Scale - the VAS is a validated pain scale that asks subjects to rate the amount of pain they are currently experiencing on a line up to 100mm (no pain is equal to 0mm and the worst imaginable pain is equal to 100mm). An improvement of 20 points from the baseline score is considered a statistically significant improvement at that visit [Gallagher, 2001].

Short-Form (36) Health Survey – the SF-36 is a patient reported survey of health that is designed to measure health status. The survey consists of eight (8) sections, where the lower the score the more disability and the higher the score the less disability [Maruish, 2009].

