At each follow-up visit, subjects will be asked on their use of any rescue medications or therapy for their knee pain. Rescue medications or therapy will include, but are not limited to, NSAIDs, physical therapy and surgical interventions. While participating in the study, subjects should refrain from taking corticosteroid and/or hyaluronic acid injections. Subjects will also be asked about their compliance with the device (ex. how long and how often the device was worn?). Research personnel will collect and record such data and note when the subject had the intervention.

Additionally, at each follow-up visit, subjects will be asked to report any changes in their knee symptoms. This change in symptoms can include, but are not limited to, pain, swelling, redness, or any overall changes in their health since the screening/baseline visit. Research personnel will collect and record such data and note when these changes occurred.

II. CHARACTERISTICS OF THE RESEARCH POPULATION

Number of Subjects

A total of one-hundred and twenty (120) patients will be enrolled in this study (60 patients assigned to each group).

Gender of Subjects

Men and women will be included in this study.

Age of Subjects

Subjects will be at least 45 years of age and no older than 75 years of age

Racial and Ethnic Origin

There are no enrollment restrictions based on race or ethnic origin.

Inclusion Criteria

- Males and females between the ages of 40-75;
- Patients suffering from symptomatic unilateral or bilateral knee OA at the medial compartment for at least six months;
- Fulfilling the ACR clinical criteria;
- Having radiographically assessed OA of the knee with a Kellgren-Lawrence grade more than or equal to grade 2; and,
- Having VAS-Pain ≥ 3 , on a scale between 0-10.
- Patients who have a shoe size between US 4 and US 12

Exclusion Criteria

- Patients suffering from acute septic arthritis.
- Patients who received a corticosteroid injection within 3 months of the study.

CONFIDENTIAL

This material is the property of the NYU School of Medicine and Langone Medical Center. Do not disclose or use except as authorized in writing by the study sponsor

- Patients who received hyaluronic acid (HA) injections within 6 months of the study
- Patients suffering from avascular necrosis of the knee.
- Patients with a history of knee buckling or recent knee injury.

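### The sample-size statement contradicts its own inputs: 60 per group gives about 99% power at 0.8 SD, not the stated 80%

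*Combined protocol and SAP*

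**What the plan says.** The sample-size paragraph appears twice: in section III under Sample Size Analysis, and in the Study Summary under Statistical Methodology.

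- **Effect.** It assumes a "reduction of pain scores of 3.0 in active group and 0 of control group with a pooled standard deviation of 3.60", and calls this an effect size of 0.8.
- **Enrolment.** "After accounting for a 10% loss to follow-up we would expect to enroll 60 patients in each group for a total of 120 patients". The 60 is therefore the number enrolled, already inflated for loss.
- **Power.** With all 60 per group counted, "the two-sided t-test will have 80% power at the 0.05 significance level to detect differences of pain score of 0.8 SD units".

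The Randomization Process section sets allocation at 1:1. Section III also refers to a Table X of power at various effect sizes. That table is not in the text available, so what it showed is unknown.

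**The concern.** An effect of 0.8 SD is large, and 60 per group is far more than a two-sided 0.05 t-test needs to detect it with 80% power. Test, alpha, group size and effect are all given, so the power is fixed by arithmetic and can be checked directly.

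Two things are at stake. The first is how sensitive the trial is taken to be. A reader would conclude that 80% power starts only at 0.8 SD, which is 0.8 × 3.60 = 2.88 points. If it really starts near 0.54 SD, a null result rules out more than the text suggests. The second is how a shortfall would be judged. On the stated figures, any recruitment gap or loss above 10% seems to take power at 0.8 SD below 80%.

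There is also a smaller inconsistency: the 60 is said to allow for 10% loss, yet the power is quoted as if nobody were lost.

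**Working it through.** **Inputs** (Sample Size Analysis, unless noted): two-sided t-test, alpha 0.05; 60 enrolled per group; 10% loss, so 60 × 0.9 = 54 evaluable per group; effect 0.8 SD, from 3.0/3.60 = 0.833; 1:1 allocation (Randomization Process); normal data.

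**Formula.** With n per group and standardised difference d, the t statistic has 2n − 2 degrees of freedom and noncentrality δ = d√(n/2). Power is the probability that |t| exceeds the two-sided 0.05 critical value.

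**1. Attempt to reproduce the stated 80%**

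| d | n per group | δ | critical t | power |
|---|---|---|---|---|
| 0.8 | 60 | 0.8 × √30 = 4.38 | 1.980 | 99.1% |
| 0.8 | 54 | 0.8 × √27 = 4.16 | 1.983 | 98.5% |
| 0.833 | 60 | 4.56 | 1.980 | 99.5% |
| 0.833 | 54 | 4.33 | 1.983 | 99.0% |

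The 80% is not reproduced. The stated figure is about 19 points too low. Rounding 0.833 down to 0.8 is slightly conservative and explains almost none of the gap.

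**2. Sample size that the stated power would need**

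At d = 0.8, 25 per group gives 79.1% and 26 gives 80.8%, so 26 evaluable are needed. Allowing for 10% loss, 26/0.9 = 28.9, or 29 enrolled per group (58 in total). The plan enrols 60, and 60/29 = 2.07 times as many.

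**3. Effect that the planned size detects with 80% power**

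- n = 54: d = 0.544, and 0.544 × 3.60 = 1.96 points.
- n = 60: d = 0.516, and 0.516 × 3.60 = 1.86 points.

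**4. Search for a reading that restores 80%**

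- One-sided test at d = 0.8: power rises further, to 99.4% (n = 54) or 99.7% (n = 60).
- Alpha 0.025 (not stated anywhere): 96.9% (n = 54) or 98.2% (n = 60).
- Sixty taken as the total: 86.1% with 30 per group, 82.2% with 27 per group.
- Efficiency loss of a rank test, taking a relative efficiency as low as 0.864: 96.9% (n = 54) or 98.1% (n = 60).
- Both pain and function required to succeed, each at 0.8 SD and independent (an assumption): 0.985² = about 97% with n = 54.
- Solving for alpha at d = 0.8: about 0.0013 (n = 54) or 0.0006 (n = 60).
- Solving for the SD with a 3.0 difference at alpha 0.05: 5.51 (n = 54) or 5.82 (n = 60), against the stated 3.60.

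None of these is a stated or natural choice that yields 80%.

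**5. What 60 enrolled does fit**

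99% power at d = 0.833 needs 53.9, so 54 evaluable, and 54/0.9 = 60 exactly. The same 60 also fits 80% power at 0.544 SD. The documents do not show which was meant.

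**The case against.** The arithmetic is not in dispute; the strongest objections concern what follows from it.

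**Safe direction may claim too much.** If 80% power was intended and the 0.8 SD is the slip, there is no surplus. At a true difference of 0.5 SD, power is 73% with 54 per group and 78% with 60. The calculation also uses an unnamed pain score, whereas the Phase I primary endpoint is WOMAC pain and function, for which no SD or target difference is given. A zero change in the sham arm is itself an assumption. This stands as a limit: the error is safe for the stated pain inputs, and adequacy for WOMAC function is not shown. It does not rescue the sentence.

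**The 0.54 SD is solved back from the sample size.** No document calls it a target or clinically relevant. That is fair, which is why the sponsor must say what was intended. As a statement of what the design delivers for one pain test at 0.05, it is true under either intent.

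**If pain and function must both succeed, joint power is the relevant quantity.** Assuming independent outcomes, 0.544 SD on each with 54 per group gives 0.80² = 64% joint power, and 80% joint power would need about 0.62 SD on each. This is a useful caution for any restated sentence.

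**The harm is modest.** 80% can be read loosely as at least 80%, Table X may have held correct figures, and no recruitment or stopping decision in the plan is tied to the power figure. All true. But a loose reading would not explain why 60 rather than 29 per group are enrolled, and the sentence remains the only visible basis for the sample size.

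**Conclusion.** The concern holds. Under the plan's own inputs, power at 0.8 SD is 99.1% with 60 per group or 98.5% with 54, against a stated 80%. The effect detectable with 80% power is 0.52 SD (60) or 0.54 SD (54), against a stated 0.8 SD. Power at 0.8 SD would fall below 80% only with fewer than 26 evaluable per group.

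This rests on normal data, equal groups, a single two-sided test of pain at 0.05, and the stated SD of 3.60 and 10% loss. Within those assumptions the error understates power, and nothing in it calls for a change in the sample size. It should be corrected because the stated power and detectable effect are not those of the design.

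**What to change.** Keep 120 patients. The sponsor should confirm which figure was intended, the power or the target difference, and then make the Sample Size Analysis and the Study Summary agree. Wording that is correct under either intent:

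> With 54 evaluable per group (60 enrolled, 10% loss), a two-sided 0.05 t-test has 80% power to detect 0.54 SD (about 2.0 points at SD 3.60), and about 98–99% power for the assumed 0.8 SD (3.0/3.60 = 0.83).

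Two additions make the sentence usable:

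- **Name the scale of the 3.0 and the 3.60.** The plan uses WOMAC, a VAS that "asks subjects to rate the amount of pain they are currently experiencing on a line up to 100mm", and a VAS criterion for entry "on a scale between 0-10", so the points have no unit as written.
- **Say what the sentence covers.** It describes one test of pain at 0.05. If alpha is to be shared with function, give the detectable effect at that alpha; for illustration, assuming 0.025 each, it is 0.60 SD, or 0.60 × 3.60 = about 2.2 points, with 54 per group. If both must succeed, give the joint power instead.

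The cost is two sentences, repeated in two places, with no change to sample size, arms, endpoints or visits.
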